### **8.3.2 Number of Migraine Days**

The exploratory endpoints for number of migraine days in this trial are as follows:

- 1) Mean change from baseline in the weekly number of migraine days during the 4-week period after the first dose of IMP
- 2) Proportion of subjects reaching at least 50% reduction, at least 75% reduction, and total (100%) reduction in the monthly average number of migraine days during the 12-week period after the first dose of IMP
- 3) Proportion of subjects reaching at least 50% reduction and at least 75% reduction in the number of migraine days during the 4-week period after the first dose of IMP for whom this level of effect is sustained throughout the 12-week period after the first dose of IMP
- 4) Mean change from baseline in the monthly average number of migraine days during the 12-week period after the first dose of IMP in subjects not receiving concomitant preventive migraine medications
- 5) Mean change from baseline in the monthly average number of migraine days during the 12-week period after the first dose of IMP in subjects receiving concomitant preventive migraine medications
- 6) Mean change from baseline in the number of migraine days during the 4-week period after the first dose of IMP

The endpoint 1) will be analyzed in the same manner as “endpoint 1)” in [Section 8.3.1](#).

The endpoint 2) will be analyzed in the same manner as “endpoint 2)” in [Section 8.3.1](#).

The endpoint 3) will be analyzed in the same manner as “endpoint 3)” in [Section 8.3.1](#).

The endpoints 4) and 5) will be analyzed in the same manner as “endpoint 4)” in [Section 8.3.1](#).

The endpoint 6) will be analyzed in the same manner as “endpoint 5)” in [Section 8.3.1](#).

### **8.3.3 Other Headache-related Endpoints**

The other exploratory headache-related endpoints in this trial are as follows:

- 1) Mean change from baseline in the monthly average number of headache days of any severity during the 12-week period after the first dose of IMP

- 2) Mean change from baseline in the monthly average number of headache hours of any severity during the 12-week period after the first dose of IMP
- 3) Mean change from baseline in the monthly average number of headache hours of at least moderate severity during the 12-week period after the first dose of IMP
- 4) Mean change from baseline in the monthly average number of days with use of migraine-specific acute headache medications (triptans and ergot compounds) during the 12-week period after the first dose of IMP in subjects who used migraine-specific acute headache medications (triptans and ergot compounds) at baseline
- 5) Mean change from baseline in the monthly average number of days with nausea or vomiting during the 12-week period after the first dose of IMP
- 6) Mean change from baseline in the monthly average number of days with photophobia and phonophobia during the 12-week period after the first dose of IMP

These endpoints will be analyzed in the same manner as [Section 8.1](#).

#### **8.3.4 Other Efficacy Endpoints**

The other exploratory efficacy endpoints collected using Electronic Patient-Reported Outcomes (ePRO) in this trial are as follows:

- 1) Mean change from baseline in quality of life, as measured by the Migraine-Specific Quality of Life Questionnaire (MSQOL) questionnaire, at each visit after IMP administration.
- 2) The health status quality of life, as measured by the EuroQol-5 Dimension, 5 response level version (EQ-5D-5L) questionnaire at 4 weeks after the final (third) dose of IMP
- 3) Mean change from baseline in subject depression status, as measured by the Two-Item Patient Health Questionnaire/Nine-Item Patient Health Questionnaire (PHQ-2/ PHQ-9) at 4 weeks after the final (third) dose of IMP
- 4) Mean change from baseline in subject work productivity and activity impairment, as measured by the Work Productivity and Activity Impairment (WPAI) at 4 weeks after the final (third) dose of IMP
- 5) Assessment of patient satisfaction, as measured by the Patient Global Impression of Change (PGIC) scale, at each visit after IMP administration.

For the endpoint 1), the transformed scores for the three domains (ie, Role Function-Restrictive, Role Function-Preventive, and Emotional Function) of MSQOL will be derived for baseline, V3/Month 1, V4/Month 2, and V5/End of treatment (Month 3). The scoring instructions are presented in [Appendix 2](#). In each domain, transformed scores will be analyzed in the same manner as [Section 8.1](#). Baseline will be the last value prior to the

first dose of IMP. Post-baseline (V3/Month 1, V4/Month 2, and V5/End of treatment [Month 3]) will be the nominal visits.

For the endpoint 2), for each domain (mobility, self-care, usual activities, pain/discomfort, and anxiety/depression), frequency distributions will be provided by scale of 1 to 5 where 1 = no problems, 2 = slight problems, 3 = moderate problems, 4 = severe problems, and 5 = extreme problems for baseline and 4 weeks after the final (third) dose of IMP in each treatment group. The ANCOVA model and Wilcoxon rank-sum test, which are described in [Section 8.1](#), will be performed for the visual analog scale. Baseline will be the last value prior to the first dose of IMP. Post-baseline (4 weeks after the final [third] dose of IMP) will be the nominal visit (V5/End of treatment [Month 3]).

For the endpoint 3), the total score will be analyzed using the ANCOVA model and Wilcoxon rank-sum test as described in [Section 8.1](#). Baseline will be the last value prior to the first dose of IMP. Post-baseline (4 weeks after the final [third] dose of IMP) will be the nominal visit (V5/End of treatment [Month 3]).

For the endpoint 4), the following scores (in percentages) will be analyzed using the ANCOVA model and Wilcoxon rank-sum test as described in [Section 8.1](#). Baseline will be the last value prior to the first dose of IMP. Post-baseline (4 weeks after the final [third] dose of IMP) will be the nominal visit (V5/End of treatment [Month 3]). The scores (in percentages) will be derived based on the WPAI questionnaire as follows:

- Percent work item missed due to health:  $\frac{Q2}{Q2 + Q4} \times 100$
- Percent impairment while working due to health:  $\frac{Q5}{10} \times 100$
- Percent overall work impairment due to health:  
 $\left\{ \frac{Q2}{Q2 + Q4} + \left[ 1 - \left( \frac{Q2}{Q2 + Q4} \right) \times \frac{Q5}{10} \right] \right\} \times 100$
- Percent activity impairment due to health:  $\frac{Q6}{10} \times 100$

For the endpoint 5), the number and percentage of PGIC responders (subjects whose PGIC score were 5 to 7) will be derived for V3/Month 1, V4/Month 2, and V5/End of treatment (Month 3). The percentage of PGIC responders will be analyzed by CMH test stratified by baseline preventive migraine medication use as described in “endpoint 2)” in [Section 8.2.1](#). Frequency distributions will also be provided by original response (scores: 1 to 7) at each visit in each treatment group.

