- CT-6.4.4.2 Change from Baseline in Monthly Number of Days of Use of Migraine-Specific Acute Headache Medication (Triptans and Ergot Compounds) in Subjects Who Used Migraine-specific Acute Headache Medication at Baseline, MMRM (FAS)
- CT-6.4.5.1 Change from Baseline in Monthly Number of Days with Nausea or Vomiting, ANCOVA and Wilcoxon Rank Sum Test (FAS)
- CT-6.4.5.2 Change from Baseline in Monthly Number of Days with Nausea or Vomiting, MMRM (FAS)
- CT-6.4.6.1 Change from Baseline in Monthly Number of Days with Photophobia and Phonophobia, ANCOVA and Wilcoxon Rank Sum Test (FAS)
- CT-6.4.6.2 Change from Baseline in Monthly Number of Days with Photophobia and Phonophobia, MMRM (FAS)
- CT-6.5.1.1.1 Change from Baseline in MSQOL - Role Function - Restrictive, ANCOVA and Wilcoxon Rank Sum Test (FAS)
- CT-6.5.1.1.2 Change from Baseline in MSQOL - Role Function - Preventive, ANCOVA and Wilcoxon Rank Sum Test (FAS)
- CT-6.5.1.1.3 Change from Baseline in MSQOL - Emotional Function, ANCOVA and Wilcoxon Rank Sum Test (FAS)
- CT-6.5.1.2.1 Change from Baseline in MSQOL - Role Function - Restrictive, MMRM (FAS)
- CT-6.5.1.2.2 Change from Baseline in MSQOL - Role Function - Preventive, MMRM (FAS)
- CT-6.5.1.2.3 Change from Baseline in MSQOL - Emotional Function, MMRM (FAS)
- CT-6.5.2.1.1 EQ-5D-5L Questionnaire - Mobility (FAS)
- CT-6.5.2.1.2 EQ-5D-5L Questionnaire - Self-Care (FAS)
- CT-6.5.2.1.3 EQ-5D-5L Questionnaire - Usual Activities (FAS)
- CT-6.5.2.1.4 EQ-5D-5L Questionnaire - Pain / Discomfort (FAS)
- CT-6.5.2.1.5 EQ-5D-5L Questionnaire - Anxiety / Depression (FAS)
- CT-6.5.2.2 Change from Baseline in EQ-5D-5L Questionnaire Visual Analog Scale, ANCOVA and Wilcoxon Rank Sum Test (FAS)

- CT-6.5.3 Change from Baseline in PHQ-9 Total Score, ANCOVA and Wilcoxon Rank Sum Test (FAS)
- CT-6.5.4.1 Change from Baseline in WPAI-Percent work item missed due to health, ANCOVA and Wilcoxon Rank Sum Test (FAS)
- CT-6.5.4.2 Change from Baseline in WPAI-Percent impairment while working due to health, ANCOVA and Wilcoxon Rank Sum Test (FAS)
- CT-6.5.4.3 Change from Baseline in WPAI-Percent overall work impairment due to health, ANCOVA and Wilcoxon Rank Sum Test (FAS)
- CT-6.5.4.4 Change from Baseline in WPAI-Percent activity impairment due to health, ANCOVA and Wilcoxon Rank Sum Test (FAS)
- CT-6.5.5.1 Proportion of Subjects with Responder in PGIC (FAS)
- CT-6.5.5.2 PGIC (FAS)

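### The SAP's WPAI overall work impairment formula has a misplaced bracket: it cannot fall below 100% and responds wrongly, or not at all, to impairment at work

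*SAP*

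**What the plan says.** SAP Section 8.3.4, endpoint 4), introduces four WPAI scores with the words "The scores (in percentages) will be derived based on the WPAI questionnaire as follows". The first is the share of work time missed, Q2/(Q2 + Q4) × 100. The second, "Percent impairment while working due to health", is Q5/10 × 100. The fourth, activity impairment, is Q6/10 × 100.

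The third, "Percent overall work impairment due to health", combines the first two. Writing a = Q2/(Q2 + Q4) and b = Q5/10, it is printed as

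{ a + [ 1 − (a) × b ] } × 100.

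The round bracket encloses only the missed-time share. The square bracket opens before the 1 and closes after Q5/10.

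The section also says that "the following scores (in percentages) will be analyzed using the ANCOVA model and Wilcoxon rank-sum test". Appendix 5 lists the output for the overall score as table CT-6.5.4.3. The SAP gives no other formula for it.

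**The concern.** An overall work impairment score should add the time lost through absence to the impairment suffered in the time actually worked. On the two component scores just above it, that is a + (1 − a) × b. The printed formula has all the pieces (the 1, the missed share and Q5/10), but its brackets make Q5/10 multiply the missed share instead of one minus the missed share.

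The SAP is the specification that the programmer follows. Coded literally, this line would give a change from baseline that ignores at-work impairment in everyone who missed no work, and counts improvement at work as deterioration in everyone who missed some. A programmer who corrected the line without saying so would depart from the SAP with no record in its Section 14.

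**Working it through.** **Inputs** (all from SAP Section 8.3.4, endpoint 4)

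- a = Q2/(Q2 + Q4), between 0 and 1 for non-negative Q2 and Q4.
- b = Q5/10, between 0 and 1. The 0 to 10 range of Q5 is inferred from Q5/10 × 100 being a percentage.
- That Q2 is time missed and Q4 is time worked is inferred from the label of the first score.

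**Formulas**

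- Printed: F = 100 × (a + 1 − ab) = 100 × [1 + a(1 − b)].
- Bracket closed after (1 − a): G = 100 × [a + (1 − a)b].

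**Range.** Since a(1 − b) lies between 0 and 1, F lies between 100 and 200, and G lies between 0 and 100. A grid of a from 0 to 1 in steps of 0.01 and b from 0 to 1 in steps of 0.1 gives the same limits.

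**Response to each component**

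- To a: both F and G change by 100(1 − b) per unit of a, so absence is handled alike.
- To b: F changes by −100a per unit of b, and G by +100(1 − a). F is flat in b when a = 0 and falls with b when a > 0. G never falls.

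**Size of the error for one subject.** F − G = 100 × (1 + a − ab − a − b + ab) = 100 × (1 − b). The printed score is too high by 100 minus the subject's at-work impairment score. The two agree only when b = 1.

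**Worked cases**

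| Q2 | Q4 | Q5 | a | b | Printed F | Re-bracketed G |
|---|---|---|---|---|---|---|
| 0 | 40 | 0 | 0 | 0 | 100% | 0% |
| 0 | 40 | 5 | 0 | 0.5 | 100% | 50% |
| 0 | 40 | 10 | 0 | 1 | 100% | 100% |
| 8 | 32 | 0 | 0.2 | 0 | 120% | 20% |
| 8 | 32 | 3 | 0.2 | 0.3 | 114% | 44% |
| 8 | 32 | 5 | 0.2 | 0.5 | 110% | 60% |
| 8 | 32 | 10 | 0.2 | 1 | 100% | 100% |
| 20 | 20 | 0 | 0.5 | 0 | 150% | 50% |
| 20 | 20 | 5 | 0.5 | 0.5 | 125% | 75% |

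**Change from baseline**

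- No absence at either visit: F = 100 at both, so its change is zero whatever happens to Q5.
- Q2 = 8 and Q4 = 32 at both visits, Q5 from 8 to 2:
  - F goes from 100 × (1 + 0.2 × 0.2) = 104% to 100 × (1 + 0.2 × 0.8) = 116%, an apparent worsening of 12 points.
  - G goes from 100 × (0.2 + 0.8 × 0.8) = 84% to 100 × (0.2 + 0.8 × 0.2) = 36%, an improvement of 48 points.
- In general, from F − G = 100(1 − b), the change in F equals the change in G minus the change in the at-work impairment score. Here: −48 − (−60) = +12.

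The last identity also holds for unadjusted group means over the same subjects. The printed score subtracts any treatment benefit on at-work impairment from the benefit on overall impairment.

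**The case against.** The algebra leaves little to dispute, so the case on the other side is about weight and certainty.

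- **Rank of the endpoint.** This is one of four WPAI scores within one exploratory endpoint. The other three WPAI formulas, the primary and secondary endpoints, the closed test and the sample size are untouched. The raw WPAI responses are listed (Appendix 6, EFF-6.2), so the score can be recomputed at any time. This stands, and it limits the priority of the point but not its correctness.
- **It may never be coded literally.** The printed structure hints at the intended term, and a score of 100% for an unimpaired worker would be conspicuous in programming checks. That is plausible, but the SAP should not depend on someone noticing, and a silent correction would leave plan and output in disagreement.
- **Direction.** The reversal applies to the at-work component only, and only when some work was missed. The score still moves the right way with absence. Whether the treatment difference itself changes sign depends on data not available here. This stands.
- **The upper limit.** A score of 200% needs Q4 = 0 and Q5 = 0. A subject who did no work has no evident answer on impairment while working, so 200% is a mathematical limit and anyone who worked at all scores below it. The lower limit of 100% needs no such special case.
- **Inference.** The SAP does not print the WPAI items, so the intended formula is inferred from the score labels. The inference is strong. That the printed formula is wrong does not depend on it: two component scores of 0% cannot yield an overall impairment of 100%.

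**Conclusion.** The formula is wrong as printed. It returns 100% to 200% for a score described as a percentage, assigns 100% to a subject with no impairment on either component, does not respond to at-work impairment when no work is missed, and responds in the wrong direction when some is. For each subject it overstates the re-bracketed score by 100 minus the at-work impairment score, up to 100 points.

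The conclusion rests on Q2, Q4 and Q5 having the meanings and ranges implied by the score labels, and on the bracket standing where the SAP text shows it. The brackets are balanced and explicit, but a glance at the SAP page will confirm this. The effect is confined to table CT-6.5.4.3. That table, produced as specified, could not be interpreted as overall work impairment.

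**What to change.** In SAP Section 8.3.4, endpoint 4), replace the overall work impairment formula with

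{ Q2/(Q2 + Q4) + [ (1 − Q2/(Q2 + Q4)) × Q5/10 ] } × 100.

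Check it against the scoring guide of the WPAI version used. Check the derivation code as well, and if CT-6.5.4.3 has already been produced from the printed formula, rerun it. If the code already uses the corrected form, record the correction so that plan and output agree. A simple programming test is that a record with Q2 = 0, Q4 = 40, Q5 = 0 must return 0%, and that no value may exceed 100%.

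The cost is one bracket in the SAP, at most one line of code and one table rerun. No new data are needed and no other analysis changes.

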### 8.3.5 Technical Computational Details for Exploratory Analysis

- Variable definitions
  - Electronic Headache Diary Data

The weekly number of days for exploratory endpoints (eg, migraine days, headache days of at least moderate severity, etc.) during the 4-week period after the first dose of IMP will be derived using the electronic headache diary data collected for the corresponding headache diary questions. The baseline value will be calculated using all data collected from the day of V1/Screening through the day before V2/Baseline and normalized to 7 days (see the following formula).

$$\frac{\sum \text{Days of efficacy variable during the screening period}}{\sum \text{Days with assessments recorded in the eDiary for the screening period}} \times 7$$

The weekly number of days for exploratory endpoints will be calculated for the subject's first 28 calendar days of diary data after the first dose of IMP. Each week is defined as 7 calendar days, with Week 1 counted from the first dose date.

If a subject has missing diary data in a week, the following method will be used to handle the missing data.

- If the subject has  $\geq 3$  days of electronic headache diary data for a week, the weekly number of days of exploratory endpoints will be prorated to 7 days for that week (see the following formula).

$$\frac{\sum \text{Days of efficacy variable during the 7 days period}}{\sum \text{Days with assessments recorded in the eDiary for the 7 days period}} \times 7$$

- If the subject has  $< 3$  days of electronic headache diary data for a week, the weekly number of days of efficacy variables will be considered as missing for that week.

The monthly average number of days/hours for exploratory endpoints (eg, headache hours of any severity, headache hours of at least moderate severity, days with use of migraine-specific acute headache medications [triptans and ergot compounds], days with nausea or vomiting, days with photophobia and phonophobia, etc.) during the 12-week period after the first dose of IMP will be derived similar to the primary endpoint using the electronic headache diary data collected for the corresponding headache diary questions. The baseline value and monthly number of days/hours for endpoints during the 4-week period after each dose (ie, for Month 1, Month 2, and Month 3) will be derived in the same manner (see [Technical Computational Details for Primary Analysis 8.1.4](#)). In the case of hours, the numerator of formula will be hours instead of days.

- Definition of headache day of any severity
 

The headache day of any severity is defined as a calendar day (0000 to 2359) with headache pain that lasts  $\geq 4$  hours of any severity or a day when the subject used acute migraine-specific medication (triptans or ergots) to treat headache of any severity or duration.

## 8.4 Subgroup Analyses

The following subgroups for the change from baseline in the monthly average number of migraine days during the 12-week period after the first dose of IMP and the monthly average number of headache days of at least moderate severity during the 12-week period after the first dose of IMP will be analyzed in the same manner as [Section 8.1](#).

- Country
- Age ( $\leq 45$ ,  $> 45$ )
- Sex

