## 3 Trial Design

### 3.1 Type/Design of Trial

This is a multicenter, randomized, double-blind, placebo-controlled, parallel-group trial in CM patients. The schematic of the trial design is shown in [Figure 3.1-1](#).

The trial consists of a 4-week screening period and a 12-week double-blind treatment period.

After obtaining written informed consent from patients, the investigator will screen them for eligibility (Visit [V] 1/Screening). Subjects who have been diagnosed with CM, and who meet all the inclusion criteria and do not fall under any of the exclusion criteria will be randomized in a 1:1:1 ratio to one of the following 3 treatment groups (V2/Baseline). The investigational medicinal product (IMP) will be administered at V2/Baseline, V3/Month 1, and V4/Month 2 as specified in the protocol Section 3.2, Trial Treatments. Subjects will also visit the trial site at 3 to 10 days and at 14 to 21 days (twice) after one of IMP administrations at either V2/Baseline, V3/Month 1, or V4/Month 2 for pharmacokinetic assessment. Subjects will also return to the trial site (V5/End of treatment) for the final assessment at 12 weeks after the first IMP administration. Subjects who are withdrawn from the trial will undergo a withdrawal assessment.

The trial includes the following treatment groups.

- TEV-48125 675/225/225 mg group

[figure not shown]
- TEV-48125 675 mg/placebo/placebo group
- Placebo group

The period of trial participation for each subject is defined as the period from the day that informed consent is obtained from the patient until the day of trial completion.

Definition of the end of trial date for individual subject:

The end of trial date for individual subject is defined as the date of V5/End of treatment for the final assessment/observation or the date of trial withdrawal. The date of trial withdrawal is defined as the date of withdrawal assessment, the date of the final assessment/observation in the double-blind treatment period, or the date of withdrawal decision, whichever comes later. For subjects who are lost to follow up, the end of trial date for individual subject is defined as the date of their last visit/contact or the date of the last attempt to contact them.

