### **3.3 Trial Population**

#### **3.3.1 Number of Subjects and Description of Population**

A total of 540 male or female (180 per group, a total of 3 groups) with CM aged 18 to 70 years, inclusive, will be enrolled in the trial. The plan is to enroll at least approximately half of the subjects in Japan. The enrollment procedure will be continued until the number of enrolled subjects reaches 540.

Continued concomitant use of some preventive migraine medications (Table 4.1.2-1 in the protocol) may be permitted, so long as a stable dose and regimen have been maintained for at least 2 consecutive months prior to informed consent, in which case the subject will be allowed to continue using no more than 1 preventive medication. However, the total number of subjects receiving concomitant preventive medication during the trial will not exceed 30% of the total sample size of the trial.

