## **4 Sample Size**

In a phase 2b trial in CM patients (Trial LBR-101-021), concerning the mean change from baseline in the monthly average number of headache days of at least moderate severity during the 12-week period after the first dose of IMP, the difference between the TEV-48125 675/225/225 mg group and the placebo group was 1.7 days and the standard deviation was 4.9 days. On the assumption that this trial will also yield a similar result to the phase 2b trial (Trial LBR-101-021), a sample size of 176 subjects per group gives more than 90% power for the trial to succeed at a significance level of 0.05 (two-sided). Based on the above and taking into account a small percentage of subjects who may be excluded from the FAS, the target sample size was determined to be 180 subjects per group and 540 subjects as the overall total included in the trial.

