- CT-6.6.1.1.1 Change from Baseline in Monthly Number of Migraine Days, ANCOVA and Wilcoxon Rank Sum Test, in Japan (FAS)
- CT-6.6.1.1.2 Change from Baseline in Monthly Number of Migraine Days, ANCOVA and Wilcoxon Rank Sum Test, in Korea (FAS)
- CT-6.6.1.2.1 Change from Baseline in Monthly Number of Migraine Days, MMRM, in Japan (FAS)
- CT-6.6.1.2.2 Change from Baseline in Monthly Number of Migraine Days, MMRM, in Korea (FAS)
- CT-6.6.2.1.1 Change from Baseline in Monthly Number of Migraine Days, ANCOVA and Wilcoxon Rank Sum Test, in Age 18-45 years (FAS)
- CT-6.6.2.1.2 Change from Baseline in Monthly Number of Migraine Days, ANCOVA and Wilcoxon Rank Sum Test, in Age >45 years (FAS)
- CT-6.6.2.2.1 Change from Baseline in Monthly Number of Migraine Days, MMRM, in Age 18-45 years (FAS)
- CT-6.6.2.2.2 Change from Baseline in Monthly Number of Migraine Days, MMRM, in Age >45 years (FAS)
- CT-6.6.3.1.1 Change from Baseline in Monthly Number of Migraine Days, ANCOVA and Wilcoxon Rank Sum Test, in Male (FAS)
- CT-6.6.3.1.2 Change from Baseline in Monthly Number of Migraine Days, ANCOVA and Wilcoxon Rank Sum Test, in Female (FAS)
- CT-6.6.3.2.1 Change from Baseline in Monthly Number of Migraine Days, MMRM, in Male (FAS)
- CT-6.6.3.2.2 Change from Baseline in Monthly Number of Migraine Days, MMRM, in Female (FAS)

- CT-6.7.1.1.1 Change from Baseline in Monthly Number of Headache Days of at Least Moderate Severity, ANCOVA and Wilcoxon Rank Sum Test, in Japan (FAS)
- CT-6.7.1.1.2 Change from Baseline in Monthly Number of Headache Days of at Least Moderate Severity, ANCOVA and Wilcoxon Rank Sum Test, in Korea (FAS)
- CT-6.7.1.2.1 Change from Baseline in Monthly Number of Headache Days of at Least Moderate Severity, MMRM, in Japan (FAS)
- CT-6.7.1.2.2 Change from Baseline in Monthly Number of Headache Days of at Least Moderate Severity, MMRM, in Korea (FAS)
- CT-6.7.2.1.1 Change from Baseline in Monthly Number of Headache Days of at Least Moderate Severity, ANCOVA and Wilcoxon Rank Sum Test, in Age 18-45 years (FAS)
- CT-6.7.2.1.2 Change from Baseline in Monthly Number of Headache Days of at Least Moderate Severity, ANCOVA and Wilcoxon Rank Sum Test, in Age >45 years (FAS)
- CT-6.7.2.2.1 Change from Baseline in Monthly Number of Headache Days of at Least Moderate Severity, MMRM, in Age 18-45 years (FAS)
- CT-6.7.2.2.2 Change from Baseline in Monthly Number of Headache Days of at Least Moderate Severity, MMRM, in Age >45 years (FAS)

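### The subgroup plan tests treatment separately within each country, age group and sex, and never estimates whether the effect differs between them

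*SAP*

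**What the plan says.** Section 8.4 is short. It opens with "The following subgroups for the change from baseline in the monthly average number of migraine days during the 12-week period", adds the corresponding headache-day endpoint, and refers back to section 8.1 for the method. The factors are country, age (45 or under, over 45) and sex.

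Section 8.1 supplies an ANCOVA with main effects only, a Wilcoxon rank-sum test and an MMRM. Each compares each active regimen with placebo. The ANCOVA and MMRM give LS mean differences with 95% confidence intervals and p-values. The only treatment interaction in the SAP is treatment-by-month, in the MMRM.

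Appendix 5 settles how section 8.4 is to be read. It lists 24 subgroup tables (CT-6.6.x and CT-6.7.x), each confined to one level of one factor. Examples are "Change from Baseline in Monthly Number of Headache Days of at Least Moderate Severity, ANCOVA and Wilcoxon Rank Sum Test, in Japan (FAS") and its companion "Change from Baseline in Monthly Number of Headache Days of at Least Moderate Severity, ANCOVA and Wilcoxon Rank Sum Test, in Korea (FAS"). No listed table compares the treatment effect between levels.

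On the size of the country groups, section 3.3.1 says: "The plan is to enroll at least approximately half of the subjects in Japan".

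**The concern.** A subgroup analysis by country is there to show whether the effect is similar in the two countries. A p-value against placebo in Japan and another in Korea answer a different question: whether each fraction of the trial can, alone, show an effect. Each fraction has far less power than the whole trial. One country can therefore reach 0.05 and the other miss it when the true effect is the same in both.

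What is at stake is the reading of the subgroup tables. Country is a term in the primary model, and many of the SAP's summaries are repeated by country, so the question of consistency will be asked. The planned output gives no direct answer, and the SAP does not say how the subgroup p-values are to be read.

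For the overall 12-week comparisons alone there are 2 endpoints × 6 subgroups × 2 regimens × 3 methods = 72 p-values. The by-month results of section 8.1.3 would come on top of these.

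**Working it through.** **Inputs**
- Effect and SD for 675/225/225 mg against placebo, primary endpoint (SAP section 4): "placebo group was 1.7 days and the standard deviation was 4.9 days".
- Planned power (section 4): "a sample size of 176 subjects per group gives more than 90% power for the trial to succeed at a significance level of 0.05 (two-sided").
- Target size (section 4): "the target sample size was determined to be 180 subjects per group and 540 subjects as the overall total included in the trial".
- Allocation (section 3.1): "randomized in a 1:1:1 ratio to one of the following 3 treatment groups".
- Country split: section 3.3.1 gives only a minimum of about half in Japan. I take 50:50 as the base case and show larger Japanese shares.

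**Step 1. Reproduce the SAP's figure.** For a two-sample t test with n per arm, the noncentrality is 1.7 / (4.9 × √(2/n)). At n = 176 the power is 90.1%, which agrees with the stated figure of more than 90%.

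**Step 2. Power within one country.** An even split of 180 per arm leaves 90 per arm in each country.
- SE of the treatment difference = 4.9 × √(2/90) = 0.730 days.
- Noncentrality = 1.7 / 0.730 = 2.33.
- Power = 63.9%.

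**Step 3. Chance that exactly one country is significant.** The countries contain different subjects, so their results are independent. With powers p_J and p_K, the probability is p_J(1 − p_K) + p_K(1 − p_J). At 50:50 this is 2 × 0.639 × 0.361 = 46%. A simulation of 200,000 trials, using the normal approximation, gave 46.0%.

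**Step 4. Vary the split, keeping a 1.7-day effect in both countries and SD 4.9**

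| Japan : Korea, n per arm | Power Japan | Power Korea | Exactly one significant |
|---|---|---|---|
| 90 : 90 | 63.9% | 63.9% | 46.2% |
| 108 : 72 | 71.8% | 54.3% | 48.1% |
| 126 : 54 | 78.3% | 43.1% | 53.9% |
| 144 : 36 | 83.5% | 30.6% | 63.0% |

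**Step 5. Vary the effect and SD at 50:50**

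| Effect (days) | SD | Power per country | Exactly one significant |
|---|---|---|---|
| 1.3 | 4.9 | 42.5% | 48.9% |
| 1.7 | 4.9 | 63.9% | 46.2% |
| 2.0 | 4.9 | 77.7% | 34.6% |
| 2.5 | 4.9 | 92.6% | 13.8% |
| 1.7 | 4.0 (assumed, if covariates cut the residual SD) | 80.9% | 30.9% |

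**Step 6. What an interaction analysis would give at 50:50**
- SE of the difference between the two country effects = 4.9 × √(4/90) = 1.03 days.
- With equal true effects, the interaction test was significant in 5.0% of the simulated trials, as it should be.
- A between-country difference of (1.96 + 0.84) × 1.03 ≈ 2.9 days is needed for 80% power.

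**The case against.** The strongest reply is that the 46% is not an error rate of the plan. A reader might infer from it that the SAP will declare heterogeneity in nearly half of trials with a common effect. The document does not support that. No rule in the SAP treats significance in one country only as a difference between countries, and the closed testing procedure in section 8.1.1 covers only the two regimens in the overall primary analysis. The figure is the rate at which two p-values fall on opposite sides of 0.05, and it misleads only if someone reads it as heterogeneity. For the same reason it should not be set against the interaction test's 5% as if the two were rival error rates. This part of the reply stands.

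It also stands that estimates with 95% CIs are already planned within each subgroup. A reader could subtract one country's estimate from the other's and combine the SEs. Under the base-case assumptions both point estimates favour active treatment in about 98% of trials (0.990²), so the direction would usually agree. But leaving the comparison to the reader is not the same as planning it, and nothing in the SAP says it will be made.

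Two further criticisms might tempt a reader and should not be made. Keeping sex in a single-sex model, or country in a single-country model, leaves the treatment differences and their SEs unchanged. Letting covariate slopes and residual variance differ by subgroup is a modelling choice with its own merits, not a fault.

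Finally, the protocol was not available for this check and may say how country consistency will be judged. That would not alter section 8.4 or the table list, which are where the SAP sets its subgroup method and which contain separate analyses only.

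**Conclusion.** The point holds as a gap in the subgroup plan. Section 8.4 and Appendix 5 provide within-subgroup comparisons with placebo and no estimate or test of a difference in effect between subgroups. The planned output therefore does not directly address consistency across the two countries.

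The 46% is an illustration of why discordant p-values are not evidence of heterogeneity. It applies to one regimen (675/225/225 mg), the primary endpoint, an even country split, a 1.7-day effect in both countries and SD 4.9. A larger Japanese share raises it; a larger true effect or a smaller residual SD lowers it. It should not be carried over to age, sex or migraine days, because the SAP gives no age or sex split and no planning effect for migraine days.

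The primary analysis and its type I error are not affected. The change is worth making because it is cheap and uses data already collected.

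**What to change.** In section 8.4, for each factor and each of the two endpoints, fit the section 8.1.1 ANCOVA once on the full FAS with a treatment-by-subgroup term. Country and sex are already in the model; for age, add the age-group main effect. From that model report:

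- the LS mean difference from placebo in each subgroup, with its 95% CI;
- for each regimen, the interaction estimate (the difference between subgroup effects) with its 95% CI and p-value.

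Label any within-subgroup p-values that are kept as descriptive, and add the new tables to Appendix 5.

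The cost is SAP wording, six models (3 factors × 2 endpoints) and their tables, with no new data, visits or subjects. The drawback is low power. With an interaction SE of about 1.03 days at 50:50, 80% power needs a between-country difference of about 2.9 days, more than the whole planned effect of 1.7. Section 8.4 should therefore say that a non-significant interaction is not proof of consistency, and that the estimate and its CI carry the interpretation.
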